Study Protocol and Statistical Analysis Plan

Title of Study: Pittsburgh and Rural Area High School Tobacco Prevention

ClinicalTrial.gov Identifier: NCT05081843

Principal Investigator: [name] [name], CHES

Date of Document: 3/16/2023

Table of Contents

	Page Number
Study Protocol	
Objectives.....	3
Design.....	3
Methods.....	3
Measures.....	4
Statistical Analysis Plan.....	6
Power and Sample Size.....	7

Study Protocol

Objectives:

Despite advances in tobacco control, tobacco use among adults continues to be a major clinical and public health challenge in the United States. This is exacerbated by the recent increase in adolescent overall tobacco use, likely prompted by the increased popularity of alternative tobacco products (ATPs) such as e-cigarettes. These products are marketed aggressively to adolescents online, and adolescents who engage with this marketing are more likely to initiate tobacco use. Considering adolescent tobacco initiation is associated with persistent nicotine addiction into adulthood, prevention efforts should be targeted at this population. Adolescent tobacco prevention programs that utilize a media literacy approach teach adolescents how to critically evaluate tobacco-related media messages. Designed for 9th grade students, the web-based media literacy program *AD IT UP* demonstrated initial feasibility and acceptability in 2011. In 2019, *AD IT UP* was updated to include ATPs and online tobacco marketing. However, the updated program has not yet been tested. The purpose of this study is to assess the feasibility and acceptability of the updated *AD IT UP* program among 9th grade students. We will conduct a cluster randomized trial comparing *AD IT UP* to usual substance use education in both high schools. Feasibility endpoints will assess completion of *AD IT UP* and associated assessments, while acceptability endpoints will assess student perceptions of *AD IT UP*. Secondary objectives are assess changes in intentions to use tobacco, attitudes, normative beliefs and tobacco media. Data collected from this study will inform a subsequent large-scale randomized controlled trial of *AD IT UP* to assess efficacy in decreasing tobacco initiation in high school students.

Design:

We will conduct a cluster randomized controlled trial (RCT) in two high schools in Pittsburgh, PA.

Methods:

[figure not shown]
Sample and Recruitment. The two high schools will be selected according to the following criteria. Schools will have an adequate number of 9th-grade students (at least 130 at each school) to power this study. Each school must have at least 4 health classes to participate in the trial. One school will be located in a rural area and the other will be located in a suburban area. Parents will be sent a letter from the school informing them of the study aims and the procedure for opting out of consent. Student assent will be obtained before the all assessments. All assessments (intervention and control) and completion of *AD IT UP* (intervention) will be completed during regular class time in the school computer lab or on student devices (i.e., ChromeBook, iPad).

Randomization. Each school will have 4 health classes. Prior to the intervention (**Figure 2**), in each school, two classes will be randomized to the intervention condition and two classes to usual education using a random number generator

Pre-test Assessment and Assignment of Identifiers. In each school, all students (intervention and control) will be assigned a unique identifier and password, which will facilitate access to *AD IT UP* (intervention students), track progress through modules (intervention students), and link to the assessments (all students).

Intervention Condition. The intervention will be the updated *AD IT UP* web-based tobacco media literacy program. *AD IT UP* is self-paced and typically takes approximately 120 minutes to complete (including pre- and post-test assessments). In previous studies of the original *AD IT UP*, students completed *AD IT UP* over a series of 3 class periods delivered 1 week apart. **Figure 2** presents this scenario.

Figure 2. Overview of Study Procedures and Data Collection.

Control Condition. Many schools develop their own substance use prevention programming, so schools' usual programming will be used to mimic what is expected in a future trial. Students in the control condition will complete assessments on similar schedules as intervention students (**Figure 2**).

Post-test and Follow-up Assessments. Following the completion of the final *AD IT UP* module, all students will complete the post-test. Follow-up assessments will be completed at 4 and 12 months after the post-test (**Figure 2**).

Measures:

Feasibility Metrics. (Primary Outcome). Data for the assessment of feasibility will be descriptive with point estimates and 95% confidence intervals. **One highly important quantitative outcome to inform a subsequent cluster randomized trial is overall retention of students.** Therefore, our main outcome of feasibility will be determined by at least 60% of students completing the pre-test, post-test, and both follow-up assessments, consistent with previous research. Other feasibility outcomes and related cut-offs are presented in **Table 1**.

Acceptability Metrics. Intervention participants will be asked to complete a series of acceptability items on the post-test assessment via close-ended 5-point Likert-type items (**Table 1**). These items are as follows: (1) I enjoyed *AD IT UP*, (2) I understood *AD IT UP*, (3) *AD IT UP* was easy to use, (4) I tried my hardest when I was doing *AD IT UP*, (5) I think *AD IT UP* would be helpful to other kids my age, (6) I would recommend *AD IT UP* to a friend, and (7) I agree with *AD IT UP*'s message.

Secondary Outcomes. Although efficacy cannot be assessed through this pilot trial, we include as part of all assessments quantitative items that will be used in a future RCT (**Table 1**), which include

susceptibility to future use of tobacco products, attitudes toward tobacco products, normative beliefs about tobacco products, and tobacco-related media literacy. These will be assessed at all 4 assessments.

- Susceptibility. Susceptibility will be assessed by asking participants whether they would use each tobacco product if it was offered to them by their best friend. Responses were *Definitely Yes*, *Probably Yes*, *Probably No*, and *Definitely No*. Separate items assessed susceptibility for cigarettes, cigars/cigarillos, e-cigarettes, and hookah. Consistent with previous literature, a participant was considered susceptible to use of an NTP if they answered anything other than “*Definitely No*” for that product.
- Attitudes. Attitudes will be assessed via 8 items asking participants to assess their agreement with statements about NTPs using a 10-point Likert-type scale (Strongly Agree to Strongly Disagree). Items include: (1) E-cigarettes are not as bad for your health as other products, (2) Using tobacco products at parties is fun, (3) Tobacco products help you deal with problems or stress, (4) Smoking helps people stay thin, (5) People who use e-cigarettes are more fun to be around than people who don’t use e-cigarettes, (6) If someone starts using tobacco products every day, it is very hard for them to stop, (7) Smoking makes a person look more attractive, (8) It would be very easy for me to get e-cigarettes if I wanted them. NOTE: An additional item (Using e-cigarettes at parties is fun) was added, making this a 9 item scale. A summary scale will be created for attitudes by calculating average scores across all items.
- Normative Beliefs. Normative beliefs will be assessed via 6 items asking participants to assess their perceptions about their friends’ acceptance of NTPs using a 10-point Likert-type scale (Very Acceptable to Very Unacceptable). Items include: (1) It is OK for people your age to smoke cigarettes, (2) It is OK for people your age to use e-cigarettes, (3) It is OK for people your age to use hookahs, (4) It is OK for people your age to smoke cigars or cigarillos, (4) A wealthy person is more likely to use tobacco products than a poor person, and (6) A successful person is more likely to use tobacco products than an unsuccessful person. A summary scale will be created for normative beliefs by calculating average scores across all items.
- Tobacco-related Media Literacy. Tobacco-related media literacy will be assessed via adapted items from the Smoking Media Literacy Scale with 8 items using a 10-point Likert-type scale (Strongly Agree to Strongly Disagree). Items include: (1) To make money, tobacco companies will do anything they could get away with, (2) Certain tobacco products are specially designed to appeal to young children, (3) Tobacco advertisers try to link tobacco products to things that people want like love, beauty, and adventure, (4) There are often hidden messages in ads for tobacco products, (5) Movies scenes with people using tobacco products in them are constructed very carefully, (6) Tobacco product ads show scenes with a healthy feel to make people forget about the health risks, (7) Most movies and TV shows that show people using tobacco products make it look more attractive than it really is, (8) When you see a tobacco product ad, it is very important to think about what was left out of the ad about potential health problems. A summary scale will be created for tobacco-related media literacy by calculating average scores across all items.

Table 1. Summary of Measures and Related Cut-offs

Measure	Assessments					Cut-offs (if applicable)
	T0	T1	T2	T3	T4	
Feasibility						
• Completion of all assessments (primary outcome)	✓	✓	✓	✓		60% of students complete all assessments
• Number of parents providing consent	✓					95% of parents provide consent
Acceptability						
• Likelihood of recommending AD IT UP to peers	✓					85% reporting “agree” or “strongly agree”
• Understanding AD IT UP	✓					85% reporting “agree” or “strongly agree”
• Whether AD IT UP would be helpful to others	✓					85% reporting “agree” or “strongly agree”
• Level of enjoyment while participating in AD IT UP	✓					85% reporting “agree” or “strongly agree”
• Agree with the message of AD IT UP	✓					85% reporting “agree” or “strongly agree”
• Ease of use of AD IT UP	✓					85% reporting “agree” or “strongly agree”
• Tried hard while using AD IT UP	✓					85% reporting “agree” or “strongly agree”
Secondary Outcome Variables						Measurement
• Intention-to-use tobacco products (cigarettes, e-cigarettes, hookah, cigars)	✓	✓	✓	✓		4-item Likert-type scale (“Definitely no” to “Definitely yes”)
• Attitudes and normative beliefs toward cigarettes, e-cigarettes, hookah, cigarillos	✓	✓	✓	✓		Attitudes: 8 items with Likert scale (Strongly Agree to Strongly Disagree)
• Tobacco-related media literacy	✓	✓	✓	✓		Norm Beliefs: 6 items with Likert scale (“Very Acceptable to Very Unacceptable) 8 items with Likert-type scale; (“SA” to “SD”)
Socio-demographic Factors						
• Age; Sex; Race/ethnicity	✓					Year; Male/Female/Other; Self-report

Statistical Analysis Plan:

Data will be analyzed using STATA.

Primary Outcome (feasibility): To answer the primary outcome of feasibility, we will calculate the number and percentage of students who completed each of the four assessments. We will answer the outcome of eligible students who participate we will calculate the number and percentage of students who were present in the classroom and (1) eligible (i.e., not opted out by parents) and (2) assent to participate (i.e., agree to participate by clicking “yes” on the assent form and completing the baseline assessment).

Acceptability: Acceptability will be assessed by calculating numbers and percentages for each of the seven overall program items. Acceptability is determined by answering “Agree” or “Strongly Agree.”

Secondary Outcomes: Although efficacy cannot be determined by a pilot trial, we will also assess changes in susceptibility, attitudes, normative beliefs, and tobacco media literacy using descriptive statistics and compare changes in these scores from pre to post-test and from post-test to follow-up between the intervention and control groups using two-sample tests of proportion. NOTE: Due to insufficient retention

of students for the 1-year follow-up assessments, changes in NTP susceptibility we assessed these changes between baseline and post-test assessments.

Power & Sample Size Justifications. Based upon a feasibility estimate of 60%, a sample size of 130 students (65 in each condition) in each school will afford the ability to estimate feasibility with a 95% confidence interval width of 0.17.

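### The plan says the pilot cannot assess efficacy, yet its secondary analysis is a set of unadjusted between-arm tests (about 7 to 14 after the retention NOTE, or 4 on the narrowest reading) with no alpha, main outcome or exploratory label

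*Combined protocol and SAP*

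**What the plan says.** The disclaimer appears twice. Under Measures, the Secondary Outcomes paragraph begins "Although efficacy cannot be assessed through this pilot trial". The paragraph of the same name in the Statistical Analysis Plan begins "Although efficacy cannot be determined by a pilot trial, we will also assess changes in susceptibility".

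The second paragraph offers descriptive statistics and then says the analysis will "compare changes in these scores from pre to post-test and from post-test to follow-up" "between the intervention and control groups using two-sample tests of proportion".

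The outcomes are defined under Measures:

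- Susceptibility: "Separate items assessed susceptibility for cigarettes, cigars/cigarillos, e-cigarettes, and hookah". Each item is reduced to susceptible or not susceptible.
- Attitudes: "A summary scale will be created for attitudes by calculating average scores across all items".
- Normative beliefs: "A summary scale will be created for normative beliefs by calculating average scores across all items".
- Tobacco-related media literacy: also an average across its items.

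On timing, Methods states "Follow-up assessments will be completed at 4 and 12 months after the post-test".

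A NOTE closes the SAP paragraph. Because too few students were retained at one year, change in susceptibility was assessed from baseline to post-test. The NOTE does not say what happens to the three scales.

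For these comparisons the document gives no alpha or sidedness, main outcome or time window, multiplicity rule, exploratory label, or between-arm estimate with an interval. The feasibility outcomes, by contrast, are to be reported as point estimates with 95% confidence intervals.

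**The concern.** A between-arm hypothesis test asks whether the programme changed the outcome. That is the question the plan says this pilot cannot answer. A test result also offers little that a later trial can use, because it conveys neither the size nor the precision of a difference.

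Both possible results invite misreading. A small p-value on one product or scale may be taken as a signal that the programme works. A large one may be taken as no effect, although nothing in the plan sizes these comparisons. Objectives says the data will inform a large randomised trial, and Measures says these items will be used in it, so readers will look to these results.

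**Working it through.** **The plan's own figure.** Power & Sample Size Justifications gives a 95% interval width of 0.17 for 60% feasibility with 130 students in a school. Check: 2 × 1.96 × √(0.6 × 0.4 / 130) = 0.168, which agrees. It is the only sizing calculation, and it concerns the precision of the feasibility estimate, not a difference between arms.

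**Counting the tests.** Four susceptibility items plus three summary scales make 7 outcomes. The contrasts are pre-test to post-test and post-test to follow-up. The latter counts as two if the 4- and 12-month follow-ups are tested separately.

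**Formulas.** With k tests at level α and every null hypothesis true, the expected number of false positives is kα. The chance of at least one is 1 − (1 − α)^k if the tests are independent. The document states no α, so 0.05 is an assumption.

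| Reading | k | 0.05k | 1 − 0.95^k |
|---|---|---|---|
| Schedule before the NOTE, both follow-ups tested: 7 × 3 | 21 | 1.05 | 66% |
| NOTE removes only the 12-month contrasts, for all outcomes: 7 × 2 | 14 | 0.70 | 51% |
| NOTE limits susceptibility to one contrast, scales keep three: 4 + 3 × 3 | 13 | 0.65 | 49% |
| All outcomes limited to baseline to post-test | 7 | 0.35 | 30% |
| Only the four binary items, baseline to post-test | 4 | 0.20 | 19% |

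The last row arises because the named method is a test of proportions, while the three scales are averages with no cut-point defined. As written, only the susceptibility items fit the method.

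**Sensitivity to α.** For 4 tests the expected count runs from 0.04 (α = 0.01) to 0.40 (α = 0.10). For 14 tests it runs from 0.14 to 1.40. Correlation between outcomes leaves the expected count unchanged but makes the chance of at least one only approximate.

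**Clustering.** Randomization assigns 4 classes in each of two schools, so 8 in all, and the planned 260 students give 260 / 8 = 32.5 per class. The tests as described make no allowance for this. The documents give no intraclass correlation, so take 0.01 to 0.05 as an assumed range:

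- Design effect 1 + (32.5 − 1) × ICC: 1.315 at 0.01 and 2.575 at 0.05.
- True level of a nominal 0.05 test, 2[1 − Φ(1.96 / √design effect)]: 0.087 and 0.222.
- Expected false positives: 0.35 to 0.89 for 4 tests, 0.61 to 1.55 for 7, and 1.22 to 3.11 for 14.

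This approximation is for a proportion at a single time. The correlation for a change could differ, and smaller classes after dropout would lower the design effect.

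**The case against.** The other side has real force.

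- **The count.** A reader might infer from the schedule that 21 tests are run and that about one false effect is expected. The current text does not support this. The NOTE cuts the susceptibility contrasts, and 21 also requires reading a single reference to follow-up as two separate contrasts. The figure describes the fullest reading of the schedule before the NOTE.
- **The disclaimer.** The sentence that introduces the tests itself disclaims efficacy, and descriptive statistics are named first. The numerical cut-offs in Table 1 concern feasibility and acceptability only, so no go/no-go rule hangs on these tests. This softens the point, but a disclaimer does not say how a p-value is to be reported or read.
- **The harm.** It is tempting to say a chance finding would decide the endpoint of the next trial. No text makes that choice depend on these tests, and Objectives already says the next trial will assess the decrease in tobacco initiation. The risk is one of interpretation.
- **The remedy.** Unadjusted 95% intervals exclude zero as often as the matching tests reject at 0.05, so moving to intervals does not control error. Ordinary intervals would also ignore class randomisation. Both statements are correct. The gain is in estimation and interpretation, and only if the intervals respect the clusters. A total ban on p-values is a preference, not something the plan's purpose requires.

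**Conclusion.** The point stands in moderate form. The plan rules out efficacy conclusions and then makes significance tests its only between-arm analysis of the secondary outcomes, without saying how the results may be used. After the NOTE, 4 to 14 tests remain, depending on how the NOTE and the method are read. That implies 0.20 to 0.70 expected false positives and a 19% to 51% chance of at least one.

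These figures assume α = 0.05, every null hypothesis true and no clustering effect; the percentages also assume independence. An expectation near one is possible under the current text, but it would come from uncorrected clustering at an assumed intraclass correlation, or from a looser α, and the documents establish neither.

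The case for change does not rest on the exact count. Even the narrowest reading leaves nearly a one-in-five chance of a spurious result, and the tests yield no estimate for planning.

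**What to change.** In the Secondary Outcomes paragraph of the Statistical Analysis Plan:

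1. Replace the two-sample tests of proportion with the estimated between-arm difference and its 95% confidence interval for each retained contrast. Use a difference in proportions for each susceptibility item, stating how change in a binary item is expressed, and a difference in mean change for each scale.
2. Use intervals that respect randomisation by class, for example from class-level summaries. With 8 classes and 2 arms these have 8 − 2 = 6 degrees of freedom, or 5 if school is also fitted.
3. State that the results are exploratory and are not evidence for or against efficacy.
4. List the contrasts that remain after the NOTE, for the scales as well as for susceptibility.

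The cost is wording and a modest reanalysis. The NOTE is in the past tense, so the susceptibility analysis appears to have been done. The change should therefore be dated and described as made afterwards, and it will act mainly on reporting. The downside is that intervals will be wide and the pilot will support no significance claim.

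### As written, the only between-arm test named for the secondary outcomes, a two-sample test of proportions, cannot be applied to three of the four, which are average scores with no cut-point

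*Combined protocol and SAP*

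**What the plan says.** The Secondary Outcomes paragraph of the Statistical Analysis Plan lists susceptibility, attitudes, normative beliefs and tobacco media literacy. It promises descriptive statistics for them and then says the analysts will "compare changes in these scores from pre to post-test and from post-test to follow-up between the intervention and control groups using two-sample tests of proportion". No other between-arm test appears in the SAP.

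The Measures section defines the outcomes as follows:

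- **Susceptibility:** yes/no for each of four products; any answer other than the firmest refusal counts as susceptible.
- **Attitudes:** eight 10-point items, with one added later, "making this a 9 item scale". The scoring rule reads: "A summary scale will be created for attitudes by calculating average scores across all items".
- **Normative beliefs:** the number of items is fixed by the statement "Normative beliefs will be assessed via 6 items", again on 10 points. Scoring follows the same pattern: "A summary scale will be created for normative beliefs by calculating average scores across all items".
- **Media literacy:** adapted items "with 8 items using a 10-point Likert-type scale". Here too the score is an average: "A summary scale will be created for tobacco-related media literacy by calculating average scores across all items".

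For feasibility and acceptability, Table 1 gives percentage cut-offs. For the secondary outcomes the same column is relabelled as measurement and holds only item counts and response anchors.

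The NOTE that ends the Secondary Outcomes paragraph cites poor 1-year retention and limits the susceptibility analysis to baseline to post-test. It gives no test or cut-point for the three scales. Methods (Post-test and Follow-up Assessments) has two follow-ups, at 4 and 12 months. Methods (Randomization) allocates two classes per arm in each of two schools.

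**The concern.** A two-sample test of proportions needs a count of students with a yes/no characteristic in each arm. A change in an average score supplies no such count unless a rule turns it into one, and the plan has no such rule for the three scales. Someone following the SAP literally would have nothing to enter into the test.

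A method or a cut-point would then have to be chosen late. The NOTE shows that 1-year retention was already known when this text was written, so any choice made now comes after at least some results were visible. What is at stake is the between-arm comparison on three outcomes that the Objectives name as secondary and whose items are intended for the later large trial.

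**Working it through.** **1. The plan's own figure.** The SAP states no figure for the secondary comparisons. Its one computed figure, a 95% CI width of 0.17 for feasibility, reproduces: 2 × 1.96 × √(0.6 × 0.4 / 130) = 0.168. It has no bearing on this point.

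**2. Outcome type against test.**

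| Outcome | Definition | Cut-point | Test of proportions usable as written |
|---|---|---|---|
| Susceptibility | yes/no per product | yes | yes, by type |
| Attitudes | average of 8 (later 9) items | none | no |
| Normative beliefs | average of 6 items | none | no |
| Media literacy | average of 8 items | none | no |

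Three of four fail.

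**3. Number of comparisons affected.**
- Pre to post-test only (if the NOTE is read as covering the scales too): 3 scales × 1 interval = 3.
- With one follow-up: 3 × 2 = 6.
- With both follow-ups compared with post-test: 3 × 3 = 9.

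**4. Is a plain t-test on change scores an adequate replacement?** Randomisation is by class: 2 schools × 4 classes = 8, four per arm, about 260 / 8 = 32.5 students each. The documents give no ICC or correlation. Assume unit SD, an overall pre-post correlation of 0.6, an ICC of 0.05, and a pre-post correlation of class effects, c, anywhere from 0 to 1. The within-class correlation is then w = (0.6 − 0.05c) / 0.95.

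- At c = 0, w = 0.632. The change score has class variance 2 × 0.05 = 0.10 and within-class variance 2 × 0.95 × (1 − 0.632) = 0.70. The true variance of the arm difference is 2 × (0.10/4 + 0.70/130) = 0.0608. The t-test estimates about 2 × (0.70 + 0.75 × 0.10)/130 = 0.0119. The ratio of standard errors is √(0.0608/0.0119) = 2.26, so the effective threshold is 1.96/2.26 = 0.87 and the false-positive rate is about 39%.
- At c = 1 class effects cancel in the change and the rate is 5%.

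So a plain t-test runs from about 5% to 39% over this range.

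**5. The class-level replacement.** Degrees of freedom: 8 − 3 (intercept, arm, school) = 5. The critical value is 2.571, and 2.571/1.96 = 1.31. The variance of a class mean of baseline-adjusted residuals (slope 0.6) is ICC × (1.36 − 1.2c) + (1 − ICC) × (1.36 − 1.2w)/32.5. The standard error of the arm difference is the square root of half of that. The average half-width is 2.571 × 0.95 × SE, where 0.95 is the mean ratio of estimated to true SE on 5 df.

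| ICC | c | Variance of class mean | SE | Half-width (SD) |
|---|---|---|---|---|
| 0 | – | 0.64/32.5 = 0.0197 | 0.099 | 0.24 |
| 0.05 | 1 | 0.008 + 0.632/32.5 = 0.0274 | 0.117 | 0.29 |
| 0.05 | 0 | 0.068 + 0.572/32.5 = 0.0856 | 0.207 | 0.51 (0.50 by simulation) |

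Simulation of this design with no true effect gives a rejection rate of 4.4% to 5.5% for the 5-df analysis in every setting tried, so it holds its level whatever c is.

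**The case against.** Four points can be put on the other side.

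- **The test could be run after dichotomising change, for example improved against not improved.** This stands in part. A reader might infer that no proportion test is possible on these scales, and the documents do not support that. What they lack is the rule, and supplying one now would be a post hoc choice. The claim is limited to the plan as written.
- **The test may have been meant only for susceptibility**, the one outcome that the NOTE discusses. The sentence refers back to all four outcomes as scores, which weighs against this. If it were so, the three scales would have no between-arm method at all, so a gap remains.
- **This is a pilot.** The Measures section says so plainly: "Although efficacy cannot be assessed through this pilot trial". This stands and limits the weight. A reader might infer that the trial's main conclusions are at risk. They are not: the primary outcome is completion of the assessments, the sample size is set on that, and descriptive statistics are planned for all four secondary outcomes.
- **A class-level analysis goes further than the mismatch of type requires.** This is partly right. The two-stage method is one choice among several, and purely descriptive reporting is consistent with the plan's disclaimer. But a replacement that ignored class would bring in another error. A reader might also infer that a plain t-test is bound to mislead, or quote a single error rate for it. That is not supported either: the rate depends on ICC and persistence values that the documents do not give.

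**Conclusion.** The rule is wrong as written for three of the four secondary outcomes (3, 6 or 9 comparisons). This rests on the text alone and needs no assumption. Susceptibility is not part of the mismatch. Its remaining gaps are smaller: the SAP does not say which proportion represents the change, and the named test takes no account of class.

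The point should be fixed, but it is secondary. It leaves feasibility, acceptability and the descriptive results untouched. The precision and error-rate figures are illustrations under an assumed ICC, overall correlation and class-effect correlation with all 260 students present; losses would widen the intervals. They support only two statements: a plain t-test is not reliably valid here, and a class-level analysis on 5 df is.

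**What to change.** **Attitudes, normative beliefs, media literacy.** Replace the test of proportions by one of the following:

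- A baseline-adjusted mean difference with 95% CI that respects randomisation by class within school. For example, regress the later score on the score at the start of the interval and on school, with no arm term; average the residuals in each of the 8 classes; compare arms on those 8 means with school in the model, on 5 df. An equivalent small-sample cluster method would also do.
- No test: report means, differences and cluster-aware 95% CIs descriptively, and say so in the SAP.

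**Follow-up.** Name the one used (4 or 12 months, or both). Where retention is too low for a comparison, report descriptively.

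**Susceptibility.** Keep a comparison of proportions at baseline to post-test, as the NOTE has it, but analyse by class and state one change quantity per product, such as the proportion susceptible at post-test adjusted for baseline.

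**Labelling.** Date the change and label it post hoc.

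**Cost.** SAP wording and a few lines of Stata, with no new data collection. Class membership must be in the linked data; this is assumed, since the protocol describes identifiers that link the assessments but does not mention class. At the same standard error, intervals on 5 df are about 31% wider than with 1.96, and the results must be presented as post hoc.

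### The pre-test to post-test comparison of secondary outcomes uses raw change and does not adjust for the pre-test score, which costs precision and leaves the result open to chance imbalance between arms

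*Combined protocol and SAP*

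**What the plan says.** The Secondary Outcomes paragraph of the Statistical Analysis Plan covers susceptibility, three averaged scales (attitudes, normative beliefs, media literacy) and two intervals of change. It will "compare changes in these scores from pre to post-test and from post-test to follow-up between the intervention and control groups", and the named method is a comparison "between the intervention and control groups using two-sample tests of proportion". No regression or covariate appears in the document.

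The data needed for adjustment are already planned:
- Under Measures, Secondary Outcomes: "These will be assessed at all 4 assessments".
- The section on pre-test assessment and identifiers links each student's assessments through a unique identifier.
- Attitudes are a mean score: "A summary scale will be created for attitudes by calculating average scores across all items". The other two scales are built the same way.
- Susceptibility is binary for each product: "a participant was considered susceptible to use of an NTP if they answered anything other than" a definite no.

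On allocation, "in each school, two classes will be randomized to the intervention condition and two classes to usual education using a random number generator". A note in the SAP says that, because of poor one-year retention, changes in susceptibility were assessed from baseline to post-test only.

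**The concern.** Subtracting the pre-test score is the same as adjusting for it with a slope fixed at 1. Self-reported scales measured twice correlate below 1, so with similar SDs the true slope is below 1 and subtraction over-corrects. This has two consequences for pre-test to post-test:

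- The contrast between arms carries more noise than the collected data require.
- If the arms happen to differ at pre-test, the arm that started worse is credited with part of its regression to the mean.

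With four classes per arm, chance differences at pre-test are plausible. The pilot is meant to inform a larger trial. A plan that never estimates the pre-post slope gives that trial no adjusted variance to plan from.

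**Working it through.** **The plan's own precision figure.** The only one is for feasibility: 60%, 130 students, 95% interval width 0.17. Wald: 2 × 1.96 × √(0.6 × 0.4 / 130) = 0.168, so it reproduces for one school with students treated as independent. No precision figure is given for the secondary outcomes.

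**Inputs from the documents.** The plan has "a sample size of 130 students (65 in each condition) in each school". Two schools give 260 students, 130 per arm. Eight classes give 260 / 8 = 32.5 students per class, four classes per arm.

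**Assumed inputs.** Pre-post correlation r, intraclass correlation (ICC) and stability of class effects over time. The documents give none of them, so ranges are shown.

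**Step 1: precision, pre-test to post-test, independent students.** In units of SD², the variance of change is 2(1 − r) and that of the baseline-adjusted score is 1 − r². The ratio of standard errors is √[2(1 − r)/(1 − r²)] = √[2/(1 + r)]. The 95% half-width is 1.96 × √(2/130) times √[2(1 − r)] or √(1 − r²).

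| r | SE ratio, change to adjusted | Half-width, change (SD) | Half-width, adjusted (SD) |
|---|---|---|---|
| 0.3 | 1.240 | 0.288 | 0.232 |
| 0.5 | 1.155 | 0.243 | 0.211 |
| 0.7 | 1.085 | 0.188 | 0.174 |
| 0.9 | 1.026 | 0.109 | 0.106 |

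For binary susceptibility, a simulation under no effect (eight classes of 32, 25% prevalence, ICC 0.02) gave ratios of 1.20 and 1.13 at latent correlations of 0.5 and 0.7.

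**Step 2: size of chance imbalance.** The SD of the arm difference at pre-test is √[(2/130)(1 + 31.5 × ICC)]. This gives 0.12 SD at ICC 0, 0.16 at ICC 0.02 and 0.20 at ICC 0.05.

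**Step 3: effect of an imbalance.** Given a pre-test difference d, the change contrast moves by −(1 − r)d. At r = 0.5 and d = 0.20 SD that is 0.5 × 0.20 = 0.10 SD towards the arm that starts worse. In simulation (r = 0.5, ICC 0.02) the slope of the estimate on the baseline difference was −0.51 for change and −0.01 for the adjusted estimate.

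**Step 4: dependence on class stability.** Steps 1 and 3 carry over to classes only if class effects regress like student scores. Simulation with eight classes of 32, overall r = 0.5, ICC 0.05:

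| Correlation of class effects over time | SE ratio, change to adjusted | Slope on d, change |
|---|---|---|
| 0.5 | 1.15 | −0.49 |
| 0.9 | 1.01 | −0.27 |
| 1.0 | 0.92 | −0.19 |

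At 0.9 the shift for d = 0.20 SD is 0.27 × 0.20 = 0.05 SD, and the adjusted estimate has a slope of +0.24, favouring the arm that starts better. At ICC 0.02 the ratio stayed above 1 throughout (1.04 with perfectly stable classes).

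**Step 5: post-test to follow-up.** The starting score is now measured after randomisation, so Step 1 does not apply. Against a follow-up score adjusted for pre-test, the SE ratio is √[2(1 − r₁₂)/(1 − r₀₂²)], where r₁₂ is the post-test to follow-up correlation and r₀₂ the pre-test to follow-up correlation. It is 1.155 at r₁₂ = r₀₂ = 0.5, but 0.894 at r₁₂ = 0.7 and r₀₂ = 0.5. It can go either way.

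**The case against.** The strongest reply is that this is a small matter in a feasibility pilot. The plan says so itself: "Although efficacy cannot be determined by a pilot trial, we will also assess changes in susceptibility, attitudes, normative beliefs, and tobacco media literacy". The primary outcome is completion of assessments, and no decision rule or sample size rests on these contrasts. The same sentence also has larger faults: a test of proportions does not suit mean scale scores, and class is ignored. All of this is true and limits the weight of the point. It does not remove it: a test of means on change that allowed for class would still use the pre-test score only by subtraction.

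Four stronger readings are tempting and are not supported:

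- **That the results are biased.** Over randomisations the change contrast is unbiased. The shift is conditional on a chance imbalance.
- **That confidence intervals are widened.** None is planned for these outcomes; the planned 95% intervals are for feasibility. The loss is in the precision of the test.
- **That the loss covers every planned comparison.** The post-test to follow-up contrast targets a different quantity, and raw change can be the more precise there.
- **That adjustment always wins.** With eight classes it need not, if class effects are very stable and the ICC is as high as 0.05.

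**Conclusion.** The point holds for the pre-test to post-test comparison. The plan compares raw changes, names no adjustment for a pre-test score it already collects, and so gives up precision under most plausible conditions. The loss in standard error is about 24%, 15% and 8% at r = 0.3, 0.5 and 0.7, assuming equal SDs and independent students. With classes, the gain from adjusting depends on the ICC and on class stability, and can vanish or reverse in the extreme case shown. A chance pre-test difference of 0.20 SD would move the estimate by about 0.10 SD at r = 0.5 if class effects regress like student scores, and by less if they are more stable. The change is worth making, but these are exploratory outcomes and the primary feasibility result is unaffected.

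**What to change.** In the Secondary Outcomes paragraph of the SAP:

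- **Attitudes, normative beliefs, media literacy.** Replace the two-sample test on pre-to-post change with a regression of the post-test score on arm, the student's own pre-test score and school. Use inference suited to eight randomised classes. After an intercept, arm and school, only 8 − 3 = 5 class-level degrees of freedom remain.
- **Susceptibility.** For each product, compare post-test status between arms adjusted for pre-test status on that product, in a matching model for a binary outcome.
- **Raw changes.** Keep them as description.
- **Any follow-up comparison.** Adjust the follow-up score for the pre-test score, and state that this estimates the arm difference at follow-up, not the change since post-test. Claim no precision gain there.

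The cost is a few sentences and modest programming, with no new data. The downside is that a model replaces a simple two-sample test. The SAP note on susceptibility is in the past tense, so any change to an analysis already done should be labelled post hoc.
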